3.8 Data Collection

Data collection begins when a pathology report is completed and deemed eligible for Oncotype testing under the Ontario criteria. The following information will be collected from the patient's electronic medical record:

- Eligibility for Oncotype DX ® (ODX) reimbursement by OHIP (histologically confirmed primary breast cancer, no prior chemotherapy, ER positive, PR positive or negative, HER2 negative, lymph node status negative or micro-invasive disease, tumour >1 cm in size (or if ≤1cm, must be grade 2/3 or have lymph node micrometastasis))

- Whether ODX was ordered and if so, the ODX recurrence score
- Data required for PREDICT 2.1 algorithm (age, menopause, ER/Her2/Ki67 status, tumor size, tumor grade, method of detection, number of positive lymph nodes)
- Which chemotherapy regimen was planned and what chemotherapy the patient received
- Time from medical oncologist visit to starting chemotherapy

Data collected will be de-identified (no patient identifiers) and will not be linked to the treating physician. Data will be entered by the CRA at each site into a secure study-specific database.

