Any study that is poised to influence physician decision making processes could have multiple alternative designs. The study group has experience in performing trials evaluating the use of different risk models in subsequent Oncotype DX ® ordering [25]. Designs could include a simple randomised trial of Predict plus or minus Oncotype DX ®. However, this would not account for confounding due to physician standard practice as it would not be possible to prevent physicians who always use PREDICT 2.1 (or Oncotype DX ®) from doing so. Alternatively, a cluster randomized trial could be performed, however, the number of different clusters (i.e. treatment centres) required for such a trial make it prohibitive. Simply put, this is a complicated question to address and any design will not be perfect. However, we feel the current proposal has the greatest chance to broadly impact on patient care, physician practice and health care economics.

Ethical Considerations

The ethics of this type of study have been considered at some length by the study team and the methodologists. The previously published Magee study (31) had a very similar study design and evaluated the effect of another mathematic model on physician decision making regarding Oncotype DX ® ordering. Requesting consent from either patients or physicians will add inherent bias to the study as the findings will then not reflect broader clinical practice. As both

PREDICT 2.1 and Oncotype DX ® are available for all eligible patients this bias could significantly impact the results and must be avoided.

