3.3 Study Procedures

Each site will have a different process for determining eligibility. Research staff at each site will be confirming Oncotype DX ® eligibility from pathology reports and will be working with New Patient booking staff (or similar) to get weekly/daily clinic lists of new patients whose tumors meet eligibly for Oncotype DX ® testing.

Patient tumours at each site will enter study screening when a complete pathology report is received. Once a patient tumour is deemed eligible, it is given a Study ID number. Pathology data is collected by study staff. At all points of the study, patients with eligible tumours will meet with their treating physician to discuss the individualised testing and treatment plan that is best for them.

Once the physician meets with the patient, we will also collect the chemotherapy treatment plan details.

After 3 months of activation, physicians will start completing a questionnaire for each new patient with an eligible tumour. Delaying the questionnaires for the first 3 months is to prevent bias.

After 6 months of activation, the physicians will receive a teaching session (Intervention) consisting of PowerPoint slides which will present an updated review on the benefits and limitations of Oncotype DX and PREDICT testing.

After this teaching session, study staff at each site will be using the pathology data to run the PREDICT tool for each patient and will provide the results to each physician prior to his/her meeting with each patient. Again after 3 months, we will re-introduce the physician questionnaire for the last 3 months of the study.

In summary:

Month 1 to 3: pathology and chemo data collected, NO physician questionnaire

Month 4 to 6: pathology and chemo data collected, PLUS physician questionnaire

Intervention teaching after 6 months of study activation

Month 7 to 9: pathology and chemo data collected, PREDICT 2.1 tool used, NO physician questionnaire

Month 10 to 12: pathology and chemo data collected, PREDICT 2.1 tool used, PLUS physician questionnaire

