3.5 Physician Participation

It is our hope that all medical oncologists that see patients with early stage breast cancer will participate so that the study captures broad clinical practice at all participating sites. There is no recruitment target for physician participation.

As described above, during months 4-6 and 10-12 of the study, physicians will receive ONE questionnaire for EACH patient that would meet the eligibility criteria for Oncotype DX ® testing. There are two versions of the physician's questionnaire (Pre-Intervention at 4-6 months and Post-Intervention at 10-12 months). This questionnaire consists of 8-9 questions and should take less than 5 minutes to complete. The questionnaire will be identified with the patient Study ID but will not record the physician's name. There are no risks to the physician bin completing the questionnaire. The study will not collect any data on individual physicians' practice patterns but instead _on each centre's practice as a whole. Completion of the questionnaire constitutes implied consent. A physician can also refuse to complete a questionnaire for a specific patient.

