4.0 STATISTICAL ANALYSIS

The primary analysis will be based on a hierarchical logistic regression analysis, with time period (pre-intervention versus post-intervention) as the primary covariate of interest. For this model, patient characteristics are considered nested within treating physician, which is nested within treatment centre. Adjustments will be performed for baseline characteristics. From our survey, it was evident that there was significant variability between centres (and between physicians) for ordering Oncotype DX. Data from Ottawa shows that approximately 15% of approximately 600 patients treated by 8 physicians have this test performed. In contrast, Kingston (5 physicians) sees around 200 eligible patients a year and Oncotype DX is ordered for around 65% of these patients,

Thunder Bay (3 physicians) sees around 70 patients a year and also tests around 65% of eligible patients, and Newmarket (3 physicians) sees around 130 eligible patients a year and Oncotype DX is ordered for around 75% of these patients. Windsor (3 physicians) and Kitchener (4 physicians) both see around 150 patients per year and orders Oncotype DX testing on 90% of eligible patients. Given concerns that use of hierarchical clusters may not sufficiently account for the substantial variability between sites, analyses will also be conducted by site, grouped by baseline rate of testing (i.e. Kingston, Thunder Bay and Newmarket will be combined, as will Windsor and Kitchener; Ottawa will be a separate group on its own). A similar analysis will be performed using hierarchical logistic regression. In addition, key supportive analyses will also be performed using a two-sample chi-square test within each site separately, comparing the change in proportion of patients for which Oncotype DX is ordered for each physician (i.e. post-intervention proportion – pre-intervention proportion for physician A, B, C, ...).

Analyses of secondary endpoints will be performed globally across all sites combined, and for each site individually. The chi-square test or Wilcoxon rank sum test will be used as appropriate for categorical or continuous endpoints respectively. Results will be presented using tables and figures, and exact confidence intervals will be constructed for outcomes of interest. Bootstrapping may be used for estimation purposes if required. All tests will be two-sided and statistical significance will be defined at the $\alpha=0.05$ level.

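### The primary model and the per-physician comparison need each patient's treating physician, but the protocol says the data will not be linked to the physician

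*Combined protocol and SAP*

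**What the plan says.** Section 3.8 (Data Collection) sets the rule for the study database: "Data collected will be de-identified (no patient identifiers) and will not be linked to the treating physician". Section 3.5 (Physician Participation) points the same way. Its sentence starting "The study will not collect any data on individual" goes on to exclude physicians' practice patterns and to allow only centre-wide practice. The same section says the questionnaire carries the patient's Study ID and not the physician's name.

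Section 4.0 (Statistical Analysis) plans three analyses that use the physician:

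- In the primary hierarchical logistic regression, "patient characteristics are considered nested within treating physician, which is nested within treatment centre".
- For groups of sites with similar baseline testing rates, "A similar analysis will be performed using hierarchical logistic regression".
- Key supportive chi-square tests within each site are described as "comparing the change in proportion of patients for which Oncotype DX is ordered for each physician", with physicians labelled by letter and the change taken as post minus pre.

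Section 4.0 also explains why the physician matters: the survey showed that "there was significant variability between centres (and between physicians) for ordering Oncotype DX".

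The sites do know who treats whom. Under section 3.3, staff run PREDICT in the second half of the study and "will provide the results to each physician prior to his/her meeting with each patient". The conflict is about what may be recorded, not about what is known locally.

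**The concern.** A model with a physician level, and a before-after difference for each physician, both need a physician label on every patient record that stays the same across the two periods. Sections 3.5 and 3.8 rule that label out, and no section describes a coded substitute. The data rule and the analysis plan cannot both be followed as written.

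Two things are at stake. First, this is a before-after comparison without a concurrent control. If physicians differ in how often they order the test, and the share of patients each one sees differs between periods, a centre's ordering rate can move although no physician has changed practice. A physician term can absorb that; a centre term cannot. Second, if the conflict is discovered only at analysis, one of two poor outcomes follows. Either the primary model is changed without a plan, or physician identifiers are added against a written commitment made without formal physician consent (sections 3.4 and 3.5).

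**Working it through.** **1. The plan's own figures.** Section 5.0 uses a simple logistic model with no physician level. I checked it with the two-proportion sample-size formula, n = [1.96·√(2p̄q̄) + 0.842·√(p1q1 + p2q2)]² / (p1 − p2)², followed by the continuity correction n/4·[1 + √(1 + 4/(n|p1 − p2|))]².

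| Group | Rates | n per period for 80% power | Plan |
|---|---|---|---|
| Ottawa | 15% to 7.46% | 301 | 300 |
| Grand River/Windsor | 90% to 77.4% | 150 | 75 + 75 = 150 |
| Newmarket/Kingston/Thunder Bay | 70% to 55.4% | 185 | 75 + 75 + 35 = 185 |

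Overall, an odds ratio of 0.67 from 50% gives 0.67/1.67 = 40.1%. With 500 patients per period the power is 88.2%, consistent with the stated value of over 80%. The figures reproduce. They neither depend on the conflict nor resolve it.

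**2. What each analysis needs.**

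| Analysis | Needs | Under 3.5 and 3.8 |
|---|---|---|
| Primary model | period, centre, physician | physician level cannot be fitted |
| Site-group models | the same | the same; Ottawa is a group alone, so no clustering level is left there |
| Per-physician change | physician label, constant over both periods | cannot be computed |
| Period effect with patients nested in centre | period, centre | can be run |
| Pooled pre/post test within a site | period, centre | can be run |

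The questionnaire cannot supply the link. It covers only months 4-6 and 10-12, physicians may decline it, and it omits the name.

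**3. Extent.** Physicians listed in 4.0: 8 + 5 + 3 + 3 + 3 + 4 = 26. Patients per period in 5.0: 300 + 75 + 75 + 75 + 35 + 75 = 635, or about 635/26 = 24 per physician. (Section 4.0 implies about 200/2 = 100 for Kingston; the 75 in 5.0 is used here.)

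**4. Illustration of shifting caseload.** The documents give no physician variance and no caseload variation, so these are assumptions. The model is logit(p) = site mean + physician effect + period effect, with normal physician effects of SD 0.5 or 1.0 and site means set to give the rates in 5.0. Grand River is taken to be Kitchener. Each setting has 20,000 runs (standard error near 5%: √(0.05 × 0.95/20,000) = 0.15 points). Two-sided 5% Cochran-Mantel-Haenszel tests stand in for the regression. Rejection by the centre-stratified test when there is no effect:

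| Caseload shares between periods | CV of shares | SD 0.5 | SD 1.0 |
|---|---|---|---|
| Redrawn independently | 0% | 5.0% | 5.1% |
| | 10% | 5.1% | 5.1% |
| | 20% | 5.3% | 6.2% |
| | 30% | 5.7% | 7.8% |
| | 50% | 7.1% | 12.3% |
| Correlation 0.5 | 30% | 5.3% | 6.5% |
| | 50% | 5.9% | 8.7% |
| Correlation 0.8 | 30% | 5.1% | 5.8% |
| | 50% | 5.3% | 6.5% |

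The physician-stratified test stays at 4.7-5.2% throughout.

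Power, centre-stratified versus physician-stratified, with equal expected caseloads and the same effect for every physician:

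- OR 0.67: 73.7% vs 74.4% (SD 0.5) and 65.6% vs 69.6% (SD 1.0).
- OR 0.50: 99.4% vs 99.4% (SD 0.5) and 98.1% vs 98.7% (SD 1.0).

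**5. Illustration of physicians who respond differently.** Let the pre/post log odds ratio vary between 26 equally sized physicians with SD tau (assumed). For 500 + 500 patients at OR 0.67, the simple variance is 1/(500 × 0.25) + 1/(500 × 0.401 × 0.599) = 0.0163, and tau²/26 is added to it.

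| tau | Variance multiplied by | True alpha if ignored | Power if accounted for |
|---|---|---|---|
| 0 | 1.00 | 0.050 | 88% |
| 0.2 | 1.09 | 0.061 | 85% |
| 0.3 | 1.21 | 0.075 | 81% |
| 0.5 | 1.59 | 0.120 | 70% |

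Without a physician label this variation cannot be estimated.

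**The case against.** The best defence is that an anonymous code was intended. Section 4.0 labels physicians by letter, 3.5 excludes only the name from the questionnaire, and the 3.8 rule stands in a sentence about de-identification. That reading is possible and softens the conflict. It does not remove it: 3.8 excludes any link, no code or key holder is described, and if a code is intended then 3.5 and 3.8 still have to say so.

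Some supporting arguments are weak, and I do not rely on them. The lists of collected items contain no physician field, but they also omit centre, study period, and the radiation and endocrine start times that 3.7 promises. The remark in the Introduction that "this would not account for confounding due to physician standard practice" concerns a rejected randomised design in which physicians could not be kept from using either tool. It does not describe a shift in who sees patients, and the documents nowhere report such a shift. The 3.5 sentence also sits in a paragraph about the questionnaire.

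It is also fair to say that the demonstrated harm is modest. The primary endpoint and a centre-level period effect survive, the lost per-physician test is only supportive, and Thunder Bay would have about 35/3 = 12 patients per physician per period. Nor is stratifying by physician a full safeguard. With physician-specific effects averaging zero (log odds ratio SD 0.3-0.5), a further check gave 7-12% rejection for the physician-stratified test and 7-11% for the centre-stratified one. These points limit the size of the problem but leave the contradiction in place.

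**Conclusion.** The concern holds, and it must be fixed. On a plain reading, the primary analysis in 4.0 uses a variable that 3.5 and 3.8 say will not be recorded. This rests on the protocol's explicit sentences and needs no assumption. What is lost is the physician level of the primary and site-group models and the whole per-physician comparison.

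The numerical consequence of falling back on centre alone is not known. In the caseload illustration, false-positive inflation is slight when shares move little or persist between periods. It exceeds 7.1% only when shares shift strongly and physicians differ widely (logit SD 1.0). Loss of power is not the main cost there: at most 4 points (65.6% vs 69.6%), provided every physician responds alike. The severity comes from a primary model that cannot be fitted as specified, not from these illustrations.

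**What to change.** Reconcile 3.5, 3.8 and 4.0 before data collection, by one of two routes.

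- **Coded physician (preferred).** Record for every patient, in both periods, a site-assigned anonymous physician code, with the key held only at the site. Amend 3.5, 3.8 and the ethics wording to say that data are linked to a coded, unnamed physician, and fit the 4.0 model with that code. Cost: one database field plus a protocol and ethics amendment. This changes a commitment made to physicians who gave no formal consent, and anonymity is weaker at Thunder Bay, Newmarket and Windsor, with 3 physicians each.
- **Centre only.** Remove the physician level and the per-physician comparison from 4.0, pre-specify the centre-level model, and state that it cannot separate a change in ordering from a change in which physicians saw the patients. Cost: wording only, but physician-level results are given up.

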4.0 STATISTICAL ANALYSIS

The primary analysis will be based on a hierarchical logistic regression analysis, with time period (pre-intervention versus post-intervention) as the primary covariate of interest. For this model, patient characteristics are considered nested within treating physician, which is nested within treatment centre. Adjustments will be performed for baseline characteristics. From our survey, it was evident that there was significant variability between centres (and between physicians) for ordering Oncotype DX. Data from Ottawa shows that approximately 15% of approximately 600 patients treated by 8 physicians have this test performed. In contrast, Kingston (5 physicians) sees around 200 eligible patients a year and Oncotype DX is ordered for around 65% of these patients,

Thunder Bay (3 physicians) sees around 70 patients a year and also tests around 65% of eligible patients, and Newmarket (3 physicians) sees around 130 eligible patients a year and Oncotype DX is ordered for around 75% of these patients. Windsor (3 physicians) and Kitchener (4 physicians) both see around 150 patients per year and orders Oncotype DX testing on 90% of eligible patients. Given concerns that use of hierarchical clusters may not sufficiently account for the substantial variability between sites, analyses will also be conducted by site, grouped by baseline rate of testing (i.e. Kingston, Thunder Bay and Newmarket will be combined, as will Windsor and Kitchener; Ottawa will be a separate group on its own). A similar analysis will be performed using hierarchical logistic regression. In addition, key supportive analyses will also be performed using a two-sample chi-square test within each site separately, comparing the change in proportion of patients for which Oncotype DX is ordered for each physician (i.e. post-intervention proportion – pre-intervention proportion for physician A, B, C, ...).

Analyses of secondary endpoints will be performed globally across all sites combined, and for each site individually. The chi-square test or Wilcoxon rank sum test will be used as appropriate for categorical or continuous endpoints respectively. Results will be presented using tables and figures, and exact confidence intervals will be constructed for outcomes of interest. Bootstrapping may be used for estimation purposes if required. All tests will be two-sided and statistical significance will be defined at the $\alpha=0.05$ level.

No interpolation will occur for missing data except in situations where the missing data is obvious (i.e. if a patient has missing Her2 status but receives trastuzumab, it can be assumed with confidence that the patient must be Her2 positive). No statistical adjustments will be made for multiple tests performed, however, appropriate caution will be made in interpretation of results, particularly for the analysis of secondary endpoints.

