5.0 SAMPLE SIZE

Sample size calculations for hierarchical regression models are difficult, as they require estimates of the number of clusters, the size of each cluster, the effect of intervention on each cluster separately and intra-cluster correlation. Without prior information, these estimates are unlikely to be accurate. Hence, statistical power and sample size calculations will be based on practical considerations.

It is hypothesized that if the use of PREDICT 2.1 decreases the odds of Oncotype DX ordering by approximately 50% or more, the usage of Predict 2.1 will be of clinical importance. It is known that approximately 300 patients are seen in a given six-month period in Ottawa, and approximately 15% of eligible patients undergo Oncotype DX testing. For the other centres, the values are 75 and 75% (Newmarket), 75 and 90% (Windsor), 75 and 65% (Kingston), 35 and 65% (Thunder Bay), and 75 and 90% (Grand River). Based on these estimates,

a simple, two-sided, $\alpha=0.05$, logistic regression model would have 80% power to detect an odds ratio of 0.46 (from 15% to 7.46%) in Ottawa, an odds ratio of 0.38 (from 90% to 77.4%) in Grand River/Windsor, and an odds ratio of 0.53 (from 70% to 55.4%) in Newmarket/Kingston/Thunder Bay. Overall, if one conservatively estimates at least 500 patients will be eligible pre-intervention and 500 patients will be eligible post-intervention, a simple logistic regression analysis would have over 80% power (2-sided, $\alpha=0.05$) to detect an odds ratio of 0.67, assuming that approximately 50% of patients undergo Oncotype DX testing in the pre-intervention period. Combined, these estimates give assurance that the sample size for this study is sufficient to capture clinically meaningful effects.

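### The within-site chi-square on each physician's change in ordering does not define a test of the period effect; a physician-stratified Mantel-Haenszel test would

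*Combined protocol and SAP*

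**What the plan says.** The primary analysis in section 4.0 is a hierarchical logistic regression with period as the covariate of interest and patients nested in physician and centre. Because the plan doubts that this handles the differences between sites, it repeats the model within groups of sites with similar baseline testing. It then adds that "key supportive analyses will also be performed using a two-sample chi-square test within each site separately, comparing the change in proportion of patients" with an order, and specifies the quantity as "post-intervention proportion – pre-intervention proportion for physician A, B, C" and so on. No small-count rule or stratified alternative is named.

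On error control, "All tests will be two-sided and statistical significance will be defined at the $\alpha=0.05$ level" and "No statistical adjustments will be made for multiple tests performed". Section 5.0 treats PREDICT 2.1 as clinically important if it "decreases the odds of Oncotype DX ordering by approximately 50% or more", an odds ratio (OR) of about 0.5. Sections 3.5 and 3.8 say that practice is recorded by centre rather than by individual physician, and that the data carry no link to the physician.

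**The concern.** A two-sample chi-square compares two independent proportions. Here it is attached to a set of three to eight differences per site, so the sentence does not determine a test. The readings it allows answer different questions: whether physicians changed by different amounts, whether each physician changed, and whether the site changed. The plan calls this analysis a key support for a model that it partly distrusts. If the choice among readings is left until the data are seen, the check could agree or disagree with the primary result for reasons unrelated to the intervention.

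**Working it through.** **The plan's own figures.** With n = [1.96√(2p̄q̄) + 0.84√(p₁q₁ + p₂q₂)]²/Δ² and the continuity correction n/4·[1 + √(1 + 4/(nΔ))]², 80% power needs 301, 150 and 185 patients per period for the three site groups. Section 5.0 implies 300, 150 and 185, so its figures reproduce. For 500 per period at OR 0.67 (50% to 40.1%), power is 88%, which fits the stated figure of over 80%. Section 5.0 gives no figure for the physician-level chi-square.

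**Inputs.** Six-month volumes and baseline rates are from section 5.0 and physician counts from section 4.0. I assume equal caseloads within a site, and that Grand River is the Kitchener site. The post rate applies OR 0.5 to the baseline odds, for example 0.65/0.35 × 0.5 = 0.929, giving 0.929/1.929 = 48.1%. The smallest expected cell is m × min(p̄, 1 − p̄), where m is patients per physician per period and p̄ is the mean of the pre and post rates. Power uses the pooled-variance normal formula.

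| Site | Physicians | Patients per period | m | Pre → post | Smallest expected cell per physician, OR 0.5 / no change | Power per physician | Power, crude site table |
|---|---|---|---|---|---|---|---|
| Ottawa | 8 | 300 | 37.5 | 15% → 8.1% | 4.3 / 5.6 | 15% | 75% |
| Kingston | 5 | 75 | 15 | 65% → 48.1% | 6.5 / 5.25 | 15% | 55% |
| Thunder Bay | 3 | 35 | 11.7 | 65% → 48.1% | 5.1 / 4.1 | 12% | 29% |
| Newmarket | 3 | 75 | 25 | 75% → 60% | 8.1 / 6.25 | 20% | 50% |
| Windsor | 3 | 75 | 25 | 90% → 81.8% | 3.5 / 2.5 | 13% | 30% |
| Kitchener | 4 | 75 | 18.75 | 90% → 81.8% | 2.6 / 1.9 | 11% | 30% |

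Section 4.0's annual volumes imply 100 per period at Kingston and 65 at Newmarket. With these, crude site power is 67% and 45%; the counts of sparse tables below do not change.

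**Reading 1: are the changes equal across physicians?** The statistic is Q = Σ(dᵢ − d̄)²/v on k − 1 degrees of freedom, where dᵢ is a physician's change, v its pooled variance and k the number of physicians. A shift common to all dᵢ cancels in dᵢ − d̄. In 40,000 simulations per site, with physicians at the site rate, Q rejects 4.8-5.4% of the time whether the common OR is 1, 0.5 or 0.25. On the log-odds scale with a 0.5 correction the rejection rate is 0.1-4.0%. On either scale a uniform fall goes undetected.

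**Reading 2: one table per physician.** Power at OR 0.5 is 11-20% (10-22% by exact enumeration). Expected cells fall below 5 for 8 + 3 + 4 = 15 of 26 physicians at OR 0.5 (Ottawa, Windsor, Kitchener), and for 3 + 3 + 4 = 10 of 26 with no change (Thunder Bay, Windsor, Kitchener). For 26 independent tests at a nominal 5%, the chance of at least one false positive is 1 − 0.95²⁶ = 0.74.

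**Reading 3: a crude pre/post table per site.** The smallest expected cells are 10.6 to 34.7 at OR 0.5 and 7.5 to 45 with no change, so the test can be run. Its weakness is that it ignores physician. The documents give no physician-level rates, so I assumed a Kingston-like site with five physicians ordering at 95, 80, 65, 50 and 35% and 15 patients each before the intervention.

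| Post-period caseloads, highest to lowest orderer | Effect | Crude rejects | Stratified Mantel-Haenszel rejects |
|---|---|---|---|
| 15/15/15/15/15 | none | about 3% | about 5% |
| 11/13/15/17/19 | none | about 6% | about 5% |
| 9/12/15/18/21 | none | about 10% | about 5% |
| 7/11/15/19/23 | none | about 15% | about 5% |
| 15/15/15/15/15 | OR 0.5 | 37% | 45% |

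If all five physicians order at 65%, power is about 57% crude and 56% stratified. With rates of 55-75% and the 11-to-19 drift, the crude test rejects 5.0% under no effect.

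**The case against.** The strongest reply is that "two-sample" and "within each site" point naturally to a site-level pre/post comparison, with physician changes shown alongside. That reading has adequate cell counts and can detect a uniform fall. This stands: a reader might infer that the analysis is unusable however it is read, and the documents do not support that. But it drops the sentence's own reference to each physician, and section 4.0 itself reports that ordering varies between physicians.

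A reader might also infer that sparse tables invalidate the per-physician chi-square. They do not: the exact type I error of the uncorrected test is 3.6-5.4%, and with no change only 10 of 26 tables are sparse. Low power and the number of tests are the real objections to that reading. The 74% figure treats the 26 tests as one independent family, whereas the plan calls them supportive and promises caution in interpretation.

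The physician spread and caseload drift are assumptions. Moderate drift does little harm, and the stratified test's power advantage disappears when physicians order alike. Finally, the primary and site-group models already allow for physician, so the plan does not depend on this check alone.

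**Conclusion.** The concern holds in a limited form. The sentence does not specify a within-site test of the period effect. Its literal reading cannot detect a uniform fall, and its per-physician reading has about 11-20% power at the effect the plan calls important. The crude site reading works, with 29-75% power. Its false-positive rate reaches about 6-15% only if physicians differ widely and caseload drifts towards low orderers. The cell counts and per-physician power assume equal caseloads.

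This is a fault in a supportive analysis. It should not be read as undermining the primary hierarchical model or the power figures in section 5.0, neither of which uses this test.

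**What to change.** Replace the sentence in section 4.0 along these lines: *Within each site, ordering before and after the intervention will be compared by a Cochran-Mantel-Haenszel test stratified by coded physician, without continuity correction; an exact conditional version will be used only where the pooled strata are too sparse. The stratified odds ratio and 95% confidence interval will be reported. Whether physicians changed differently will be examined separately by a Breslow-Day or exact homogeneity test.*

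The text change is small, but it has a condition. The test needs an anonymous physician code on each patient record, and sections 3.5 and 3.8 appear to rule that out. The primary model needs the same code, because it nests patients within physician, so those sections must be reconciled with section 4.0 in any case.

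There is a modest cost in power where the exact version is used, because it is somewhat conservative. As a guide, a continuity-corrected stratified test in the assumed 35-95% setting has about 38% power at OR 0.5, against 45% uncorrected. No change to sample size or follow-up is needed.
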